7.8 Documentation

All adverse events occurring after the subject has signed the informed consent will be fully recorded in the subject's eCRF. Each event will be described in detail, along with start and stop dates, severity, relationship to IMP, action taken and outcome.

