13.6.7.1 Adverse events

The verbatim terms used in the eCRF by investigators to identify adverse events will be coded using the Medical Dictionary for Regulatory Activities (MedDRA). Intervention-emergent adverse events are adverse events with onset after the intervention phase or that are a consequence of a pre-existing condition that has worsened since treatment start. All reported adverse events will be included in the analysis. For each adverse event, the percentage of subjects who experience at least one occurrence of the given event will be summarized by treatment arm. In addition, comparisons between intervention groups will be provided as appropriate.

Summaries, listings, datasets, or subject narratives may be provided, as appropriate, for those subjects who die, or who experience a severe or a serious adverse event.

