#### 8.11.1.1 Treatment-emergent adverse events (TEAEs)

Treatment-emergent adverse events are any event with onset date/time between the study treatment start date and the study treatment end date, limits included.

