### **10.12.1 Adverse events**

Adverse events (AEs) will be summarized for treatment emergent adverse events (TEAEs). TEAEs are defined as AEs that occur on or after the day of the first dose. MedDRA terminology will be used to classify all AEs with respect to system organ class (SOC) and preferred term (PT).

A summary of subjects with TEAEs will be presented for each treatment group. The summary will include counts and percentages for subjects who experience at least one AE, overall and by SOC and PT. This will be repeated for severe TEAEs, related TEAEs and serious TEAEs. Severity will be captured as Grade 1 through Grade 5 with Grades 3-5 categorized as severe. Related will be captured

as: none, unlikely, possibly or probably, with related = possibly or probably. Serious will be captured with the standard serious adverse event (SAE) criteria.

The summary tables will be presented in descending order according to the incidence in the 'All' group (e.g., SOC and PT within each SOC with the highest number of occurrences will appear first). Equal frequency of different SOC/PTs will be sorted in alphabetical order of the SOC/PT.

Subjects who report the same PT on multiple occasions will be counted once for the preferred term under the highest severity when summarizing by severity, under the closest relationship to the drug when summarizing by relationship, under most serious when summarizing by seriousness.

Separate summary tables by SOC and PT will be provided for: TR-TEAEs, SAEs, and AEs leading to premature treatment discontinuation.

Individual subject listings will be provided on SAF.

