#### **10.12.1.1 Subgroup analysis**

TEAEs, SAEs, AEs related to the study drug and AEs leading to premature treatment discontinuation will be tabulated on SAF by preferred term (PT) by treatment phase as follows:

- **Days of dosing:** all AEs occurred on same date/visit of treatment but only during or after administration of study drug (with time on or after treatment administration). Week 1 D1 (Dose 1), Week 1 D5 (Dose 2), Week 2 D8 (Dose 3), Week 2 D12 (Dose 4), Week 3 D15 (Dose 5), Week 3 D19 (Dose 6), Week 4 D22 (Dose 7), Week 4 D26 (Dose 8), Week 5 D29 (Dose 9), Week 5 D33 (Dose 10), Week 6 D36 (Dose 11), Week 6 D40 (Last dose 12);

This information will be pooled in summary table, i.e. all AEs occurred on/after all doses: first, second etc. until last dose; as well as will be summarized separately, i.e. AEs occurred on/after each dose: on/after first dose, on/after second dose etc. and until on/after last dose.

- **Non-dosing days:** (a) all AEs with the date different from treatment administration date/visit defined above and until Week 10 Follow-up visit. (b) all AEs which occurred prior to study drug administration (with time before administered dose) on dosing days.

This information will be pooled in summary table, i.e. all AEs occurred between doses: first and second, second and third etc. until Week 10 Follow-up visit (EOS) or until Early Termination (ET) whatever comes earlier, as well as will be summarized separately, i.e. split by periods between doses: Dose 1 - Dose 2, Dose 2 - Dose 3, Dose 3 - Dose 4, Dose 4 - Dose 5, Dose 5 - Dose 6, Dose 6 - Dose 7, Dose 7 - Dose 8, Dose 8 - Dose 9, Dose 9 - Dose 10, Dose 10 - Dose 11, Dose 11 - Dose 12, Dose 12 | last administered Dose - EOS | ET.

In case of missing dates, the rules defined in Section 11.3.3 will be applied. In case of missing time of the AE or the treatment administration on the same day, the AE will be considered as occurred after the treatment administration, meaning will be summarized in 'Days of dosing' category.

Frequency statistics will be presented by treatment group. The summary tables will be presented in descending order according to their incidence in the active treatment group of 'Days of dosing' treatment phase (e.g., individual preferred term with the highest number of occurrences appear first) sorting ties alphabetically.

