##### ***11.1.1.2 Study treatment start date (Day 1)***

Study treatment start date is the date of Week 1 D1 as collected in the "Date of visit" field in the section "Medical Events checks" when "LSD / Placebo administered" is ticked "Yes" in "Study Drug Administration" section.

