### **11.1.1.3 Study treatment end date (EOT)**

This is the last day of study drug intake, which is the date reported in “Date of visit” field in section “Medical Events checks” (for each Visit form) when “LSD / Placebo administered” is ticked “Yes” in “Study Drug Administration” section.

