### **11.1.1.8 Baseline value**

Except where otherwise specified, baseline is defined as the last value measured or assessed before or on the date of the first dose of investigational drug administration at Visit 1. If the baseline visit takes place on the date of the first dose of investigational drug, then time should be considered, i.e. baseline date/time < first dose date/time.

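### Adverse events that begin on Day 1 before the first dose count as treatment-emergent, and the by-phase tables have no correct row for them

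*SAP*

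**What the plan says.** The SAP defines a treatment-emergent adverse event (TEAE) twice.

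- Section 8.11.1.1: "Treatment-emergent adverse events are any event with onset date/time between the study treatment start date and the study treatment end date, limits included". Section 11.1.1.2 supplies the lower limit: "Study treatment start date is the date of Week 1 D1 as collected in the" visit-date field, with no time attached. Section 11.1.1.3 supplies the upper limit: "This is the last day of study drug intake".
- Section 10.12.1: "TEAEs are defined as AEs that occur on or after the day of the first dose". This wording has no upper limit.

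The footnotes to layouts T4, L10 and L24 repeat the date limits of 8.11.1.1.

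Two other SAP sections use the clock on dosing days. For a baseline visit on the day of first dosing, 11.1.1.8 says "then time should be considered, i.e. baseline date/time < first dose date/time". For the by-phase adverse event tables, 10.12.1.1 puts into the non-dosing category "all AEs which occurred prior to study drug administration (with time before administered dose) on dosing days".

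The protocol's own definition (13.6.7.1) begins "Intervention-emergent adverse events are adverse events with onset after the intervention phase" and adds worsening of a pre-existing condition. It matches neither SAP version.

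**The concern.** Events before the first dose can be in the data. Protocol 7.8 says "All adverse events occurring after the subject has signed the informed consent will be fully recorded", and Protocol 6.2.3 lists adverse event recording among the Day 1 activities done before dosing. A pre-dose blood sample is drawn that day, and Protocol 7.1.3 names the risks of venipuncture. Discomfort from that draw, or a headache that starts on the way to the clinic, would be treatment-emergent although no drug had been given.

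The SAP is also at odds with itself. On the same morning, a vital sign taken before dosing is a baseline value, while an adverse event before dosing is attributed to the treatment period. The flag matters because it feeds the overall, severe, related and serious TEAE summaries, and the TEAE by-phase table is marked as a key deliverable.

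**Working it through.** The plan gives no figure on this point, so there is nothing to reproduce. The check applies the rules to test events and then sizes the effect.

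**Inputs.** The limits come from SAP 8.11.1.1, 10.12.1, 11.1.1.2 and 11.1.1.3. The arm size of 26 is in Protocol 13.6.4 and SAP 2.1.1. Assumed for illustration: first dose on Day 1 at 10:00, last dose on Day 40.

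**Rules.**
- A (8.11.1.1): first-dose date ≤ onset date ≤ last-dose date
- B (10.12.1): onset date ≥ first-dose date
- C (clock-time start, upper limit as in A): onset date/time ≥ first-dose date/time, and onset date ≤ last-dose date

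| Onset | A | B | C |
|---|---|---|---|
| Day −1, 15:00 | no | no | no |
| Day 1, 08:30 (pre-dose) | **yes** | **yes** | **no** |
| Day 1, 11:00 (post-dose) | yes | yes | yes |
| Day 20 | yes | yes | yes |
| Day 40 | yes | yes | yes |
| Day 41 | no | yes | no |
| Day 55 | no | yes | no |

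Moving from A to C changes only the Day 1 pre-dose event. The last two rows show a separate disagreement between A and B at the closing end.

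**By-phase tables.** SAP 10.12.1.1 lists Week 1 D1 as a dosing day and sends pre-dose events on dosing days to the non-dosing category. That category is then split into periods, the first of which runs from dose 1 to dose 2; the programmer note to layout T27 repeats this. An event before dose 1 is admitted by the rule but belongs to none of the periods. The programmer must either drop it or put it in a period that follows dose 1.

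**Size.** If a subject's only TEAE is a Day 1 pre-dose event, the arm's rate rises by 1/26 = 3.8 percentage points. A subject with any other TEAE does not change the overall rate.

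For a range, let p be an arm's true TEAE rate and q the chance that an otherwise event-free subject has a Day 1 pre-dose event, equal in both arms. The recorded rate is p + (1 − p)q, so the arm difference becomes (p1 − p0)(1 − q). The documents give none of these values. Assuming 80% against 40% and q of 5% to 10%:
- Difference: 0.40 × 0.95 = 0.38 and 0.40 × 0.90 = 0.36, so 40 points becomes 38 to 36.
- Expected subjects reclassified, active: 26 × 0.20 × q = 0.26 to 0.52.
- Expected subjects reclassified, placebo: 26 × 0.60 × q = 0.78 to 1.56.
- Total: about 1 to 2 in the whole trial.

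**The case against.** One defence is that 8.11.1.1 speaks of an onset date and time, which might imply a clock comparison. It fails: the limit is a date, the limit is included, and 10.12.1 refers to the day of the first dose.

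The better defence concerns weight, and most of it stands. The window at issue is a few hours on one morning, before either arm has received drug. Protocol 13.6.7 plans no inference on safety. Related events are tabulated separately, and listing L10 shows start date and time, so a reader could spot such a case. A day-level rule also fits the SAP's habit of resolving doubt towards treatment, for example by counting missing intensity as severe. But that habit deals with missing information. Here the time may be known and is ignored.

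Three stronger inferences should not be drawn.
- **That the arm difference is materially diluted.** The 80%, 40% and q values above are assumptions. Nothing in the documents supports a 5% to 10% chance of a new onset in the hours before dosing.
- **That this is why the period rows fail to add up to the pooled count.** Layout T27 counts subjects. A subject with the same term in two periods appears twice in the rows and once in the pool, whatever the start rule. The defect is the missing row.
- **That wash-out symptoms would flow in.** Onset decides, not when the symptom is noticed. Protocol Appendix 1 requires most listed drugs to be stopped at least 5 half-lives before Day −1, and adverse events are also recorded at Baseline. Most such symptoms would carry an earlier onset date and already fall outside the window.

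**Conclusion.** The point holds on the text: both SAP definitions open the window on the calendar date of the first dose, and no section removes Day 1 pre-dose events. It also leaves a specification gap in the by-phase tables. Severity is minor. The effect is probably small and there is no reason for it to favour one arm, since neither has been dosed. The 3.8 points per subject applies only where the pre-dose event is the subject's sole TEAE, and the documents do not allow the number of such subjects to be computed. This is a free improvement rather than a threat to the safety conclusions.

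The two definitions agree only at the opening end. At the closing end, 8.11.1.1 stops at the last-dose date while 10.12.1 runs on. Events from the day after the last dose to the Week 10 visit (target Day 70) are therefore classified differently, and the by-phase table itself runs to Week 10. Correcting the lower limit alone would leave that larger inconsistency in place.

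**What to change.** - In SAP 8.11.1.1, 10.12.1 and the footnotes to T4, L10 and L24, set the lower limit as onset date/time ≥ first-dose date/time.
- On Day 1, if the event time or the dose time is missing, count the event as after dosing. SAP 10.12.1.1 already uses this convention. It also covers partial start dates that SAP Table 8 sets to the treatment start date.
- List Day 1 pre-dose events as pre-treatment adverse events and leave them out of the TEAE by-phase tables.
- In the same edit, choose one upper limit and use a single TEAE definition throughout, noting in SAP Appendix D how it differs from Protocol 13.6.7.1.

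The cost is SAP wording and one comparison in the derivation. No new data are needed: L10 already shows the event start time, Protocol 5.5 requires the time of each administration to be recorded, and 10.12.1.1 already compares the two.

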### 13.1.4 Layout T4

Study MMED007 - Deliverables: <Deliverables>

Table <Number of table>

<Title>

Analysis set: <analysis set>

<Medical history/Concomitant diseases>

System Organ Class / Preferred Term	MM-120 N=xx N (%)	Placebo N=xx N (%)	All N=xx N (%)
ALL SYSTEM ORGAN CLASSES			
Total number of subjects with at least one <medical and psychiatric events   AE>	xx (yy.y)	xx (yy.y)	xx (yy.y)
System Organ Class 1 <preferred term1> <preferred term2>	xx (yy.y) xx (yy.y) xx (yy.y)	xx (yy.y) xx (yy.y) xx (yy.y)	xx (yy.y) xx (yy.y) xx (yy.y)
System Organ Class n <preferred term1> <preferred term2>	xx (yy.y) xx (yy.y) xx (yy.y)	xx (yy.y) xx (yy.y) xx (yy.y)	xx (yy.y) xx (yy.y) xx (yy.y)

System Organ Class and Preferred terms are based on MedDRA 25.1 dictionary.

Program: [program\\_name.sas](#), Produced on yyyy-mm-dd hh:mm (CET),

Snapshot date: yyyy-mm-dd, Draft/final

Page x of x

Note for programmer: display medical history and concomitant diseases in separate pages.

Please use 'System Organ Class and' only in tables by SOC and PT and not in those only by PT.

Please add footnote 'Treatment-emergent adverse events are events with onset date/time between the study treatment start date and the study treatment end date, limits included.' In the tables with treatment-emergent AEs.

Please add footnote 'A Serious Adverse Reaction (SAR) is a serious adverse event that is determined to be related to the study treatment' to the table with Summary of serious adverse reaction (SAR) by system organ class (SOC) and individual preferred term (PT).

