### 13.2.11 Layout L10

Study MMED007 - Deliverables: <Deliverables>

Listing <Number of listing>

<Title>

Analysis set: <analysis set>

Subject ID	Active Treatment	System organ class/ Preferred term/ Reported term	Start date/ Time/ Study Day*	End date/ Time/ Duration (days)	Treatment Emergent**	Serious	Severity	Relation. to study drug	Action Taken With Study drug		Outcome
									With Study drug	Outcome	
xxx	xxx	xxxxxx/ xxxxxx/ xxxxxx	ddmmyy/ yyy/ Hh:mm	ddmmyyyy/ Hh:mm	Yes/No	No/Yes: xxxx	xxxx	xxxx	xxxx	xxxx	xxxx

\*Study day is the day of the event relative to the treatment start date.

\*\*Treatment-emergent adverse event is any event with onset date/time between the study treatment start date and the study treatment end date, limits included.

System Organ Class and Preferred terms are based on MedDRA 25.1 dictionary.

Program: [program\\_name.sas](#), Produced on yyyy-mm-dd hh:mm (CET),

Snapshot date: yyyy-mm-dd, Draft/final

Page x of x

*Note for Programmer: Severity = Intensity of AE.*

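### The SAP's treatment-emergent definitions drop the protocol's worsening limb without declaring it, so a pre-dose event that worsens on treatment and stays on one record is left out of the key TEAE tables

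*SAP*

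**What the plan says.** **Protocol.** Sections 12.1 and 13.6.7.1 give the same two-limb definition of an intervention-emergent event. One limb is onset. The other covers events "that are a consequence of a pre-existing condition that has worsened since treatment start". Read literally, the onset limb places onset later than the whole intervention phase, when later than its start is evidently meant. Section 7.8 sets the collection period: "All adverse events occurring after the subject has signed the informed consent will be fully recorded in the subject's eCRF". Events with onset before the first dose are therefore in the database.

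**SAP.** There are two definitions.
- Section 8.11.1.1: "Treatment-emergent adverse events are any event with onset date/time between the study treatment start date and the study treatment end date, limits included". The closing date is defined in 11.1.1.3: "This is the last day of study drug intake".
- Section 10.12.1: "TEAEs are defined as AEs that occur on or after the day of the first dose". This has no closing date.

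The outputs follow 8.11.1.1. The programmer note to Layout T4 requires this footnote on the TEAE tables: "Treatment-emergent adverse events are events with onset date/time between the study treatment start date and the study treatment end date, limits included". The flag in the adverse event listing, Layout L10, reads: "Treatment-emergent adverse event is any event with onset date/time between the study treatment start date and the study treatment end date, limits included".

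Appendix D lists twelve changes from the protocol's analyses, and Appendix B lists the changes between SAP versions. Neither mentions removal of the worsening limb.

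**The concern.** The protocol and the SAP classify one kind of event differently: an adverse event that is already present before the first dose and gets worse during treatment. The kind is realistic in this trial. Collection starts at consent, and screening can run for up to four weeks before Baseline. Protocol 5.5.1 has subjects taper ADHD, anxiety, depression or mood medication in that interval, and the adverse event definition in 7.6.1 covers mood symptoms and altered sleep. Protocol 7.2 regards the main safety concerns with this drug class as psychological.

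What is at stake is the content of the tables most readers will use. TEAESOC and TEAEPTTP are marked as key deliverables in SAP 12.8.1 and 12.8.1.1; the all-AE tables AESOC and AEPT are not. The SAP is also inconsistent within itself. Section 8.11.3.2 calls a laboratory abnormality treatment-emergent when it reaches a worse category than at baseline, so a shift from H to HH counts. A shift from mild to severe on a single adverse event record does not.

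**Working it through.** The plan gives no figure on this point, so there is none to reproduce. The check applies each definition to constructed cases and then sizes one misclassified subject.

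**Step 1: apply the definitions.** The protocol's onset limb is read as evidently intended, that is, onset after the start of the intervention phase. The nominal last dose is Day 40.

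| Case | Protocol 12.1 / 13.6.7.1 | SAP 8.11.1.1, T4, L10 | SAP 10.12.1 |
|---|---|---|---|
| A. Mild anxiety from Day -10, severe on Day 5, one record | Emergent (worsening limb) | Not emergent | Not emergent if occurrence means onset; no worsening criterion |
| B. Same course, but a new record starting Day 5 | Emergent | Emergent | Emergent |
| C. New event with onset Day 45 | Emergent (no end stated) | Not emergent | Emergent |

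Case A is the gap. Case B shows that the gap depends on how worsening is recorded. Protocol 7.8 asks for start and stop dates and severity for each event, but gives no rule on whether an increase in severity opens a new record. Case C shows that the two SAP definitions also disagree on the end of the window. SAP 10.12.1.1 tabulates TEAEs on non-dosing days up to the Week 10 visit, which fits the open-ended definition and not the one printed under the tables.

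**Step 2: see where a case A event still appears.** By their titles in SAP 12.8.1, the all-AE, SAE and discontinuation tables are not restricted to TEAEs. The event stays in AESOC, AEPT and the listing, where L10 would flag it as non-emergent. The all-AE tables mix worsened pre-dose events with unchanged ones, so the protocol's category cannot be recovered from them.

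**Step 3: size.** Input: 26 subjects per arm (SAP 2.1.1). For k affected subjects in an arm, the shift in that arm's rate is k/26:
- k = 1: 1/26 = 3.8 points
- k = 2: 2/26 = 7.7 points
- k = 3: 3/26 = 11.5 points

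For a preferred term, this assumes the subject has no other counted record of that term. For the any-TEAE rate, it assumes the subject has no other TEAE at all. The documents give no rate of such events, so the values of k are illustrative and k = 0 is possible.

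**Step 4: effect on the arm comparison.** If a and b subjects should be counted on MM-120 and placebo, and k is missed in each arm, the difference is (a - k)/26 - (b - k)/26 = (a - b)/26, which is unchanged. The difference moves only if the numbers missed are unequal, and the documents do not say which arm would have more.

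**The case against.** The strongest reply is that the protocol does not describe case A. Its second limb speaks of an event that results from a worsened condition, and such an event would ordinarily have its own on-treatment onset and be counted by the SAP. Pre-existing conditions have a separate CRF section with an ongoing box (SAP 8.3). Protocol 7.6.1 also treats a clinically significant change from baseline as an adverse event, with mood and sleep among its examples, so worsening insomnia or anxiety may be an event in its own right. SAP 10.12.1 expects subjects to report the same preferred term more than once. A rule on new records may sit in the eCRF completion guidelines or the annotated CRF, which are not among the documents reviewed.

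Much of this stands: the loss depends on recording practice. It does not close the gap. With the onset limb read as intended, a second limb that covered only events with on-treatment onset would add nothing to the first. Nothing in either document requires a new record, so under the SAP's rule the classification of case A depends on site habit.

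A reader might also infer more than the documents support:
- **That the MM-120 rate is understated relative to placebo, biasing the comparison towards no harm.** This needs more worsening on MM-120 than on placebo, which is an assumption. The medication taper comes before randomization and should balance across arms on average. Equal omission leaves the difference unchanged.
- **That the events disappear from safety reporting.** They remain in the all-AE tables and the listing, and a serious event remains in SAESOC, itself a key deliverable. Protocol 13.6.7 plans no statistical inference on safety.
- **That a known share of subjects is affected.** No pre-dose event rate is given.

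**Conclusion.** The mismatch is real and undeclared. The worsening limb is absent from both SAP definitions, the T4 footnote and the L10 flag, and the two SAP definitions conflict on when the window ends. Followed as written, the SAP leaves a pre-dose event that worsens on its original record out of TEAESOC and TEAEPTTP.

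The size cannot be stated beyond 3.8 points per affected subject per arm, under the conditions given above. The total number is unknown and may be zero, and so is the direction of any bias between arms. The conclusion rests on two assumptions: that some worsening was kept on original records, and that the protocol's second limb was meant to add something to its onset limb. This is a classification fault in key safety tables that should be corrected. It does not touch the primary endpoint.

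**What to change.** - Use one TEAE definition in SAP 8.11.1.1, SAP 10.12.1, the T4 note and the L10 footnote: onset on or after the first dose, or onset before the first dose with increased intensity, or becoming serious, on or after the first dose. State the end of the window in the same sentence.
- Name the severity scale used to judge increased intensity, because 8.11.1.2 uses three levels and 10.12.1 uses Grades 1 to 5.
- Apply the definition by reviewing adverse events with pre-dose onset that were ongoing at first dose, blinded to arm if that is still possible. A new instruction to sites is probably too late: SAP version 2.0 is dated 19.12.2023, was written for the CSR, and already comments on observed medians (Appendix B).
- Correct the onset limb in Protocol 12.1 and 13.6.7.1 to refer to the start of the intervention phase.
- List any remaining departure in Appendix D.

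The cost is wording, a small programming change and a short review. If the eCRF holds a single intensity per record, the date of worsening may have to come from source notes. TEAE counts may rise slightly.
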